8.2. Time Matched Rituximab Concentration (TMRC) Analysis

A time matched blood sample (approximately 5 mL) will be collected before administration of study drug on Day 1 and Day 15, and at Weeks 4, 8, 12 (EOS/ET) visit for the estimation of concentration of rituximab

A listing of time matched rituximab concentrations (TMRC) will be provided. Also, summary statistics by treatment arm and visit will be provided by mean, standard deviation (SD), minimum (min), maximum (max), median and quartiles.

8.3. Analysis of Exploratory Endpoints

Possible intercurrent events (IcEvs) in this study are presented in [Table 2](#).

Table 2: Intercurrent events

Label	Intercurrent Event
IcEv1 (Death)	Death due to any cause
IcEv2 (Prohibited therapy)	Use of prohibited therapy that interferes with the evaluation of immunogenicity
IcEv3 (Missed/Discontinuation of IMP)	Missed/Discontinuation of IMP without receiving the second infusion as scheduled at Day 15 due to any reasons
IcEv4 (COVID-19/SARS-CoV-2 infection)	Incidence of COVID-19/SARS-CoV-2 infection after infusion.

Attributes for the immunogenicity and safety estimands with strategies for handling IcEvs are presented in [Table 3](#). Safety estimands are presented here together with the immunogenicity estimands for ease of reference to estimands.

Table 3: Immunogenicity and Safety Estimand

Estimand Label	Estimand 1 (Immunogenicity)
Estimand Description	Immunogenicity will be evaluated using incidence of positive ADA including Nab in subjects with active RA who are currently in treatment with US-rituximab or EU-rituximab and are eligible for the subsequent treatment course with US-rituximab or EU-rituximab. The development of ADA is measured while on study over up to 12 weeks or until death or use of prohibited therapies with impacts on immunogenicity assessments whichever is earliest, regardless of treatment discontinuation due to any other reasons.
Target Population	Subjects with active RA who are eligible for the subsequent treatment course with US-rituximab or EU-rituximab and would meet other study entry criteria and receive at least 1 dose of study treatment
Endpoint	Development of ADA, including titer and NAb
Treatment Conditions	Test: two 1000 mg infusions of DRL_RI Reference: two 1000 mg infusions of US-rituximab/EU-rituximab
Population-Level Summary	Incidence of ADA, including titer and NAb
Intercurrent Event (IcEv) Strategy	
IcEv1 (Death)	While-on-treatment strategy (measurements of the endpoint up until the time of the intercurrent event)
IcEv2 (Prohibited therapy)	While-on-treatment strategy
IcEv3 (Missed/Discontinuation of IMP)	Treatment policy strategy
IcEv4 (COVID-19/SARS-CoV-2 infection)	Treatment policy strategy
Rationale for Strategies	The immunogenicity assessment is to evaluate the incidence of ADA over a period whilst on study over up to 12 weeks and prior to the occurrence of intercurrent events without use of prohibited therapies. Hence, while on treatment policy is used to utilize the data until death or data prior to the prohibited medication. A treatment policy strategy is used for assessing immunogenicity irrespective of missed/discontinuation of IMP and COVID-19/SARS-CoV-2 infection.

Estimand Label	Estimand 2 (Safety - AEs)
Estimand Description	Counts and percentages of eligible subjects who are treated and would develop TEAES or SAEs A treatment policy strategy is used for assessing safety irrespective of any intercurrent events. Death is included as part of the endpoint (composite strategy).
Target Population	Subjects with active RA who are eligible for the subsequent treatment course with US-rituximab or EU-rituximab and would meet other study entry criteria and receive at least 1 dose of study treatment
Endpoint	Occurrence of TEAEs, SAEs, and AEs leading to withdrawal
Treatment Conditions	Test: two 1000 mg infusions of DRL_RI Reference: two 1000 mg infusions of US-rituximab/EU-rituximab
Population-Level Summary	Percentage of subjects who develop each type of AEs
Intercurrent Event (IcEv) Strategy	
IcEv1 (Death)	Composite strategy
IcEv2 (Prohibited therapy)	Treatment policy strategy
IcEv3 (Missed/Discontinuation of IMP)	Treatment policy strategy
IcEv4 (COVID-19/SARS-CoV-2 infection)	Treatment policy strategy
Rationale for Strategies	Deaths would be analyzed as part of the safety endpoint as per normal practice. A treatment policy strategy is used for assessing safety irrespective of any other intercurrent events.

9. Safety Analysis

Safety estimands are defined in [Table 3](#). Since, all the intercurrent events follows treatment policy there will be no change in the counts summarized. Hence, single table will be generated as per safety endpoints and none for Estimand 2. All safety analysis will be performed on the safety population unless otherwise specified.

9.1. Adverse Events

An adverse event (AE) is defined as any untoward medical occurrence in a subject, or clinical investigation subject administered a pharmaceutical product, and which does not necessarily have a causal relationship with this treatment. An AE can therefore be any unfavorable and unintended sign, symptom, or disease temporally associated with the use of a study treatment, whether or not related to the study treatment.

A treatment-emergent AE (TEAE) is defined as an AE that meets any of the following conditions:

- Begins on or after the first dose of study drug.
- Begins before the first dose of study drug and worsens in severity on or after the first dose of study drug.

A SAE is defined as any untoward medical occurrence that at any dose results in death, is life-threatening, requires inpatient hospitalization or prolongation of existing hospitalization, results in persistent or significant disability/incapacity, is a congenital anomaly/birth defect or important medical event.

All adverse events will be classified by System Organ Class (SOC) and Preferred Term (PT) according to the Medical Dictionary for Regulatory Activities (MedDRA, Version 23.0 or higher or available latest version). The severity of the AE will be graded based on the Common Terminology Criteria for Adverse Events (CTCAE) v5.0 or available latest version. AEs that are missing a severity will be imputed as 'Severe' but will be presented in the listing with a missing severity.

All TEAEs and AE for rescue medication will be summarized and presented in a listing for the safety population.

9.1.1. Incidence of Adverse Events

Summaries of the total number of TEAEs and the number and percentage of subjects with at least one TEAE will be provided by treatment arm. Adverse events will be presented by SOC and PT. For subject's counts, subjects who report more than one

event will be only be counted once for each level of SOC and PT. Percentages will be based on the number of subjects in the safety population.

An overview summary of the total number of events (e), and the number of subjects and percentage of subject with any of the following will be presented.

i)	TEAE,
ii)	Serious TEAE.
iii)	Drug-Related TEAE,
iv)	Drug-Related Serious TEAE,
v)	TEAE leading to treatment discontinuation,
vi)	Serious TEAE leading to treatment discontinuation,
vii)	TEAE leading to Death
viii)	Drug-Related TEAE leading to Death
ix)	TEAE of grade 3 or higher
x)	TEAE Classified as Hypersensitivity Reactions,
xi)	TEAE Classified as Infusion Related Reactions,
xii)	TEAE Classified as Anaphylactic Reactions,
xiii)	TEAE Classified as Hypersensitivity Reactions leading to treatment discontinuation,
xiv)	TEAE Classified as Infusion Related Reactions leading to treatment discontinuation,
xv)	TEAE Classified as Anaphylactic Reactions leading to treatment discontinuation,
xvi)	Serious TEAE Classified as Hypersensitivity Reactions leading to treatment discontinuation,
xvii)	Serious TEAE Classified as Infusion Related Reactions leading to treatment discontinuation,
xviii)	Serious TEAE Classified as Anaphylactic Reactions leading to treatment discontinuation,

All TEAEs will be summarized and presented in a listing for safety population.

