5.7 Blinding

A double-blind design is employed so that both the investigators and the subjects will be unaware of the treatment assignment during the whole study. Moreover, study center staff involved in study treatment administration and study endpoints assessments, CRO personnel, and the sponsor team including study statistician will be blinded to the treatment received. The clinical laboratories analyzing the blood/plasma samples and the concentration/incidence of anti-rituximab antibodies will also be blinded to the treatment assignment. A team from the CRO, independent to the clinical monitoring group, shall be responsible for maintaining drug accountability logs. An unblinded study coordinator or pharmacist at each site will be responsible for maintaining drug accountability as well as for dispensing. The final CSR will include all end points, after all subjects complete the Week 12 (EOS/ET) visit and the database up to the Week 12 (EOS/ET visit) has been locked. The study will be unblinded after the database up to the EOS/ET visit has been locked. The subsequent follow-up data from Week 12

to 26 will be reported as an addendum to the final CSR and for the data up to and including the Week 12 or ET visit.

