6.3.1.2 Recording of Adverse Events

Any relevant observations made at the screening visit (prior to signing the ICF) are to be recorded as a preexisting condition. For the purposes of this study, any detrimental change in the subject's condition, after signing the ICF and up to completion of the 26-week study period, should be considered as a TEAE/SAE.

The following variables will be recorded for each AE: verbatim/AE description and date for AE start and stop, severity, seriousness, causality rating, whether or not the AE caused the subject to discontinue, action taken with the study treatment, and the outcome. If the severity of the event changes, the event with the highest severity will be recorded.

Serious AEs and TEAEs will be recorded starting after signing of the ICF. All SAEs and AEs have to be recorded, whether or not considered causally related to the study treatment or to the study procedure(s).

All ongoing nonserious AEs should be followed up until resolution or stabilization or the EOS/ET visit, whichever occurs first, with the exception of any ongoing treatment-related nonserious AEs that should be followed until that AE is stabilized, resolved, or, in the investigator's opinion, the AE is unlikely to resolve due to the subject's underlying condition.

All ongoing SAEs should be followed up until resolution or stabilization/or until a pre-defined outcome is reached.

Note: Outcome information received on on-going SAE beyond the date of data base lock, will be captured in safety database and reported as follow-up report in the form of individual case safety report.

At any time after the additional follow-up visit, if an investigator learns of an SAE that can be reasonably related to study treatment, he/she should promptly notify the sponsor/designee.

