11.4 Final Report

Whether the study is completed or prematurely terminated, the sponsor will ensure that the CSR is prepared and provided to the regulatory agency(ies) as required by the applicable regulatory requirement(s). The sponsor will also ensure that the CSR in marketing applications meet the standards of the ICH Harmonised Tripartite Guideline E3: Structure and Content of Clinical Study Reports.

Data until Week 12 will be analyzed and reported in the final CSR after all subjects complete Week 12 visit (EOS/ET). The subsequent follow-up data from Week 12 to Week 26 will be reported as an addendum to the final CSR and for the data up to and including the Week 12 or ET visit.

Where required by applicable regulatory requirements, an investigator signatory will be identified for the approval of the CSR. The investigator will be provided reasonable access to statistical tables, figures, and relevant reports and will have the opportunity to review the complete study results.

Upon completion of the CSR, the sponsor will provide the investigator with the full summary of the study results.

12 Financing and Insurance

The sponsor shall carry an insurance policy to cover compensation of subjects' health injuries arising from the study. If a subject incurs a study-related injury, the subject may be treated (and other necessary measures taken) at the study site and/or another medical institution. If it is necessary to compensate for the treatment, the sponsor will cover the cost. The sponsor shall not impose on the subject the burden of proving the causal relation between the study and the injury.

If any of the following is confirmed, the sponsor may refuse or restrict the payment of the compensation:

1. A serious GCP or protocol deviation by the investigator or sub-investigator (except deviation medically necessary to avoid an immediate hazard to the study subjects).
2. Intentional act or negligence on the part of the investigator or sub-investigator or malpractice thereby.
3. Injury caused by unlawful act or delinquency of a third party.
4. Injury caused by intentional act or negligence of the subject.

If compensation becomes necessary for a study-related injury, the site will promptly notify the sponsor and will cooperate with the sponsor and its insurer (or their legal representatives) in their handling thereof.

13 Reference List

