3.1. Overall Study Design and Plan

This study is a phase 3, randomized, double-blind, parallel group, multicentre study to assess the immunogenicity and safety of two 1000 mg IV infusions of DRL₁RI or continued treatment with Rituxan[®] or MabThera[®] in approximately 140 subjects (70 per treatment arm) in transitioning to biosimilar Rituximab (DRL₁RI) or continued treatment with Rituxan[®] or MabThera[®].

Baseline is defined as the last available value prior to the first dose of study drug administration. For Vital Sign timepoint assessment are scheduled on Day 1 and Day 15, if the time is missing then Day 1 Pre-dose will be considered as baseline.

The study will include screening period (Days -14 to 0) and a double-blind period (Day 1 to Week 12), which consist 2 weeks of treatment period and 10 weeks of follow-up period for safety and immunogenicity. An additional follow-up visit will be conducted at Week 26 to evaluate safety and to perform a serum pregnancy test in women of childbearing potential (WOCBP).

Re-screening will be allowed for those subjects who do not meet the criteria for participation in this study (screen failure) at the investigator's discretion, following discussion with the sponsor designee medical monitor.

Eligible subjects will be randomized in permuted blocks in 1:1 ratio by interactive web response system (IWRS) to receive either two 1000 mg infusions of DRL_RI (Arm A) or US-rituximab/EU-rituximab (Arm B) on Day 1 and Day 15. Randomization schedule will be stratified by region (US/EU).

[figure not shown]
Subjects having signed the informed consent form (ICF) versions prior to the protocol version 3.0, Amendment 2 need to re-consent to continue participating in the study after Week 12 through Week 26. If a subject does not re-consent for further study participation after Week 12, then his/her study data up to Week 12 will be collected and the subject will be discontinued from the study.

Study procedures include physical examination, vital signs measurement, clinical laboratory assessments, AEs, and concomitant medication. All subjects completing the study at Week 12 or those discontinuing the study before Week 12 will attend an EOS/early termination (ET) visit. Furthermore, subjects completing the follow-up at Week 26 or discontinued after Week 12 will attend Week 26/early termination (ET) visit.

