4.2. Randomization, Stratification, and Blinding

An interactive web response system (IWRS) will be used to administer the randomization schedule. CI Biostatistics department has generated the randomization schedule using SAS® software version 9.4 for IWRS, which links sequential subject randomization numbers to treatment codes. The randomization schedule is stratified by region (US/EU). It has also used an appropriate block size, which will not be revealed until the database lock.

Randomization plan document was prepared before the generation of randomization schedule. The randomization code is computer-generated and kept by a statistician independent from the project team.

A double-blind design is employed so that both the investigators and the subjects will be unaware of the treatment assignment during the whole study. Moreover, study center staff involved in study treatment administration and study endpoints assessments, CRO personnel, and the sponsor team including study statistician will be blinded to the treatment received. The clinical laboratories analyzing the blood/plasma samples and the concentration/incidence of anti-rituximab antibodies will also be blinded to the treatment assignment. A team from the CRO, independent to the clinical monitoring group, shall be responsible for maintaining drug accountability logs. An unblinded study coordinator or pharmacist at each site will be

responsible for maintaining drug accountability as well as for dispensing. The final study report will include all data including all end points after all subjects have completed Week 12 (EOS/ET) visit and subsequent additional follow-up data from Week 12 to 26.

Emergency unblinding can be made for any subject without affecting the double-blind nature of the study. Subject treatment information may only be accessed in the event of an emergency and out of necessity to know the identity of the allocated study treatment in order to institute appropriate therapeutic management. In such situation once a randomization code has been broken for a subject, he/she must be withdrawn from the study. The investigator must inform the medical monitor/designee in writing within 24 hours.

Subjects who withdraw or discontinue before or after the randomization their subject identification number will not be re-used.

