5.1. Disposition

A summary of screen failures will be provided including the number and percentage of subjects for the following categories: subjects screened, subjects who failed screening and the primary reason for screen failure (“Inclusion/Exclusion criteria not met” “IN01” to “EX18” and “Withdrew consent”).

A listing of screen failures will be presented.

A summary of the analysis populations includes the number and percentage of subjects in safety and immunogenicity populations. This summary will also include the number and percentage of subjects for the following categories:

- Subjects in the safety population.
- Subjects excluded from safety population along with reasons.
- Subjects in the immunogenicity population
- Subjects excluded from the immunogenicity population along with reasons.
- Summary of disposition will include:
 - Subjects who completed week 12 visit.
 - Subject who completed study treatment.
 - Subject who discontinued study treatment along with reasons.
 - Subjects who terminated study prior to week 12 along with reasons.
 - Subjects who did or didn't reconsent for week 26.
 - Subject completed study (week 12) with protocol version 2.
 - Subjects who completed week 26 visit.
 - Subjects who discontinued prior to week 26 visit along with reasons.

Summary will be provided for all randomized subjects and all percentages will be based on the number of subjects randomized.

Subject disposition data will be presented in a listing for all randomized subjects.

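### The SAP sets no end to the TEAE period although follow-up is 12 or 26 weeks, SAP 4.2 departs from the protocol's Week 12 report without declaring it, and no separate AE output identifies events after rituximab re-dosing

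*SAP*

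**What the plan says.** **Event window and denominator.** Under SAP 9.1 an event is treatment-emergent if it "Begins on or after the first dose of study drug", or if it started earlier and then worsened. No end date is given. SAP 9.1.1 adds: "Percentages will be based on the number of subjects in the safety population". SAP 3.2 limits the immunogenicity endpoint to 12 weeks but measures safety for as long as the subject is on study. Protocol 6.3.1.2 collects adverse changes "up to completion of the 26-week study period, should be considered as a TEAE/SAE".

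**Unequal follow-up.** SAP 3.1 says: "If a subject does not re-consent for further study participation after Week 12, then his/her study data up to Week 12 will be collected", after which the subject is discontinued. SAP 5.1 has a disposition row for a second group: "Subject completed study (week 12) with protocol version 2". All other subjects are planned to be followed to Week 26.

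**Reporting.** Protocol 5.7 says: "The final CSR will include all end points, after all subjects complete the Week 12 (EOS/ET) visit", with database lock and unblinding at that point. Protocol 11.4 continues: "The subsequent follow-up data from Week 12 to Week 26 will be reported as an addendum to the final CSR". Protocol 3.1.1 agrees. SAP 4.2 instead describes a final study report with all data "after all subjects have completed Week 12 (EOS/ET) visit and subsequent additional follow-up data from Week 12 to 26". SAP 10.1 lists one change from the protocol, the addition of estimands.

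**Re-dosing.** Protocol 3.1.1 allows rescue therapy, and rituximab re-dosing where the local label permits, after Week 12. It leaves the safety analysis of these subjects to the SAP. SAP 7.1 excludes label-based re-dosing from rescue medication. Table 14.1.6.3 and Listing 16.2.4.12 report re-dosing as medication. The AE outputs tied to later therapy, Table 14.3.1.2.11 and Listing 16.2.7.11, name rescue only.

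**The concern.** Incidence of TEAEs and SAEs is a primary safety endpoint. A proportion of subjects with an event has a meaning only over a stated period. If some subjects contribute 12 weeks and others 26, the crude percentage is neither a 12-week nor a 26-week risk. It moves with the share who continue and is hard to set beside other studies.

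The conflict over reporting decides which problem arises. One report to Week 26 gives mixed follow-up. A Week 12 report plus addendum gives a sound first set of tables. The SAP's denominator rule would then count subjects in the addendum who were no longer being observed.

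For re-dosed subjects, a reaction to a later rituximab course would appear among the TEAEs of the randomised course, and no table would mark it as such.

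**Working it through.** **1. Is there a period anywhere?** SAP 9 states no Week 12 cut, no split at Week 12 and no exposure adjustment. No AE table title in SAP 12.2 names a period. The table shells are not shown, so they cannot settle the matter. SAP 5.1 counts the follow-up groups, but only in disposition.

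**2. How much can follow-up length matter?** The plan has no figure of its own to reproduce here, so this is an illustration.

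Inputs:
- Protocol 1.1.1.4: 94 infections per 100 patient-years, and 4 per 100 patient-years for infections that were serious or needed IV antibiotics.
- Protocol 3.1.1: 70 subjects per arm.
- Assumed: a constant rate, and 52 weeks per year.
- Not in the documents: the share *f* followed to Week 26, which is therefore varied.

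Expected count by week *w*: m = rate × w/52. Independent events: P = 1 − exp(−m). Events clustered within subjects (negative binomial, assumed shape k): P = 1 − (1 + m/k)^(−k).

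For rate 0.94, m = 0.94 × 12/52 = 0.2169 at Week 12 and 0.94 × 26/52 = 0.4700 at Week 26.

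| Assumption | By Week 12 | By Week 26 | Gap (points) | Subjects of 70 |
|---|---|---|---|---|
| Independent | 19.5% | 37.5% | 18.0 | 13.7 vs 26.2 |
| k = 1 | 17.8% | 32.0% | 14.1 | 12.5 vs 22.4 |
| k = 0.5 | 16.5% | 28.2% | 11.7 | 11.5 vs 19.7 |

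Mixed percentage = P12 + f × (P26 − P12). From k = 0.5 to independent events:
- f = 25%: 19.4% to 24.0%
- f = 50%: 22.3% to 28.5%
- f = 75%: 25.3% to 33.0%

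For the rate of 0.04, risk is about 0.9% by Week 12 and 1.9% to 2.0% by Week 26.

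**3. The addendum route.** Over Weeks 12-26 (14 weeks), m = 0.94 × 14/52 = 0.2531, so P = 1 − exp(−0.2531) = 22.4% among subjects actually followed. Divided by the whole safety population, this becomes f × 22.4%: 5.6%, 11.2% or 16.8% for f = 25%, 50% or 75%.

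**4. Between arms.** If f were 40% in one arm and 60% in the other (assumed), identical risk would show as 19.5 + 0.4 × 18.0 = 26.7% against 19.5 + 0.6 × 18.0 = 30.3%, a difference of 3.6 points. This shows what an imbalance would do. It does not predict one.

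**5. How many might be re-dosed?** The documents do not say. As a rough proxy, take the minimum intervals in inclusion criterion 3 (16 weeks US, 24 weeks EU). Counted from Day 1, the time left before Week 26 is 26 − 16 = 10 weeks (US) and 26 − 24 = 2 weeks (EU). Counted from Day 15, it is 26 − 18 = 8 and 26 − 26 = 0. Six of the seven countries in SAP 6.1 are in the EU, although the split of subjects is not given. The number may be small.

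**The case against.** **The protocol already implies a Week 12 cut.** AE tables run on the Week 12 lock would stop there. The sentence in SAP 4.2 sits in a section on randomisation and blinding and might loosely mean the CSR plus its addendum. This stands in part: a reader might infer that the percentages will certainly be mixed, and the documents do not establish that. The two texts still differ, SAP 10.1 is silent, and the addendum route leaves the denominator problem of step 3.

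**Crude incidence while on study is an ordinary choice in a descriptive study, and SAP 5.1 will report how many continued.** True. A reader could then see that follow-up was mixed, but could not recover a 12-week or 26-week risk from the table.

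**Re-dosed subjects are covered.** A reader might infer that no AE output includes them. That is wrong: they are in the safety population, hence in the general TEAE tables and listings, and case-by-case review is possible. The SAP also states treatment policy for safety, although re-dosing is not among its listed intercurrent events. What is missing is an output that identifies events after re-dosing.

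**The numbers are mostly assumption.** Agreed. They concern infections, not all TEAEs, and the shapes and continuing shares are assumed. A reader might take 37.5% as an upper limit. Protocol 1.1.1.4 says infections were more frequent in the first 6 months of treatment, so an average rate need not bound the early risk.

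**Bias between arms.** A reader might infer this too. Treatment is randomised and double-blind, and the documents give no reason to expect different continuation by arm.

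**Conclusion.** The point holds as a gap in specification that is cheap to close. SAP 9.1 and 9.1.1 leave the TEAE period open while follow-up ends at Week 12 for some subjects and Week 26 for others. SAP 4.2 disagrees with protocol 3.1.1, 5.7 and 11.4, and the difference is undeclared. The separate safety treatment of re-dosed subjects that the protocol left to the SAP is incomplete.

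Mixing follows only if SAP 4.2 is applied as written; dilution follows if the addendum uses the SAP 9.1.1 denominator. In the illustration the two follow-up lengths differ by 11.7 to 18.0 points for any infection and about 1 point for serious infection. These depend on the assumed rate pattern and clustering and are not bounds.

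The harm is mainly to interpretation, with some room for chance imbalance at 70 per arm. Infusion-related, hypersensitivity and anaphylactic reactions to the Day 1 and Day 15 infusions are little affected, because they occur close to the infusion.

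**What to change.** 1. In SAP 9, define the main AE tables (14.3.1.1 and the 14.3.1.2 series) as TEAEs with onset from first dose to the Week 12/ET visit. Show Week 12-26 TEAEs separately, with subjects entering that period as denominator. Keep a cumulative while-on-study table, so that the SAP 3.2 safety endpoint and the added 6-month follow-up stay visible.
2. Reconcile SAP 4.2 with protocol 3.1.1, 5.7 and 11.4, or declare the change in SAP 10.1.
3. Extend Table 14.3.1.2.11 and Listing 16.2.7.11, or add parallel ones, to flag TEAEs with onset after rituximab re-dosing, including infusion-related, hypersensitivity and anaphylactic reactions. Present them by study treatment actually received, as protocol 7.4.6 requires, and by re-dosed product if the eCRF records it. Keep treatment policy for the main analysis.

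The cost is SAP wording and repeat runs of existing table programs. AE start dates are collected, and re-dosing is already summarised and listed. The downside is a few more tables with small counts.
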